- Weight instability (weight change >5% in last 6 months)
- History of any organ transplant, including islet cell transplant
- Current or prior infection with HIV, hepatitis B or hepatitis C, or transaminases >2x ULN
- Any condition, medical or otherwise that would, in the opinion of the investigator, prevent complete participation in the study, or that would pose a significant hazard to the subject
- History of substance abuse within the 12 months prior to screening

Screening: A phone screen will be followed by provision of the consent form and a screening/enrollment visit at the outpatient CTRC. This visit will include the consent process, history, physical exam, non-fasting screening labs [β -HCG, HbA1c, metabolic panel, TSH, urine microalbumin, and CBC], detailed menstrual history for women, and a DEXA scan for body composition and estimation of caloric needs.

Study design:

T1D subjects (n=30) will have a fixed order of treatment (placebo-metformin) and will be given their first medication after screening is complete and eligibility confirmed. Medications (metformin 500, 1000mg and identical placebo) will be dispensed by the pharmacy and the subject will be blinded to the fixed order of the medications to avoid biased treatment effects throughout the intervention period. As in previous Barbara Davis Center (BDC) metformin studies, this study will use the CTRC pharmacy to dispense the active drug and placebo. Both are provided by Caraco manufacturer. My colleagues at the BDC already purchased tooling for the Caraco brand placebo tablets and the company has agreed to make more placebo tablets for this study as necessary to cut out the upfront cost of tooling.

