Subjects will be instructed to take study drug at 500mg at bedtime for the first week, 500 mg twice daily for the second week, 500/1000mg daily for one week and 1000mg twice daily for the remainder of the 6 week period. Subjects who fail to tolerate an uptitration will be held at the prior dose for an additional 3 days and then retried. Subjects who have not reached at least 500 mg BID dosing by the end of week 3 will be withdrawn from the study. Thus, final metformin dosing will be 500 BID or 1000 BID. During the last three days of each treatment phase, subjects will be placed on a standardized typical diabetic diet (40% carbohydrate, 35% fat, 25% protein; based on CACTI food records) for three days prior to late evening admission on day 3 to the CTRC. Overnight admission is critical to ensure that all subjects are in the same state prior to each testing session. Remaining pills will be turned in to allow a pill count as a measure of compliance. Subjects will be transitioned to an insulin drip for overnight glucose control using the protocol previously used for CTRC protocol 1499 (see appendices for starting doses and titration schedule). Inpatient studies (baseline labs, vascular studies, biopsies, and hyperinsulinemic euglycemic clamp) will be performed the following day (Figure 4). After a two week to two month washout period, the full cycle will be repeated with the second intervention. Women will be tested at the same time in their menstrual cycle (day 4-9) after each intervention period. Allowing up to 2 months between interventions is necessary to allow this type of scheduling with the possibility of a missed cycle due to scheduling conflicts. The study timeline and detailed visit schedule are as follows:

Screening:

- Visit 1: Screening visit - consent process, H&P, non-fasting labs, DEXA, dietary questionnaire

Stage 1 (Study drug A, Placebo):

- Visit 2: Stage 1 start visit (day A1) – Insert CGM and receive instruction on use and download, pick up Placebo, Instructions from PI re med dosing and insulin dose self-adjustment
- Visit 3: Stage 1 CGM follow-up visit (day A8) – in person CGM download and reinsertion of sensor for the next week. Review glucoses with PI.
- Visit 4: Stage 1 prestudy day visit (day A39) – pick up three day diet and receive instructions on insulin dosing and times for the pre-study day. Accelerometer set-up
- Visit 5: Admission for Placebo study day (Days A42, 43) – see below

2 weeks- 2 months wash-out

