Stage 2 (Study drug B, Metformin):

- Visit 6: Stage 2 start visit (Day B1) - Insert CGM and receive instruction on use and download, pick up Metformin, Instructions from PI re med dosing and insulin dose self-adjustment
- Option for one week visit 6b if desired for first repeat CGM insertion
- Visit 7: Stage 2 prestudy visit (Day B39) - pick up three day diet and receive instructions on insulin dosing and times for the pre-study day. Accelerometer set-up
- Visit 8: Admission for Metformin study day (Days B42,43) - see below

During the study visits procedures will include the following: baseline blood draws for inflammatory, metabolic, endothelial, and thrombotic markers; heart rate variability; vascular function and stiffness by flow-mediated dilation (FMD), plethysmography, brachial artery distensibility, and pulse wave velocity (PWV), and augmentation index (AI); insulin sensitivity by 2-stage hyperinsulinemic clamp (8, 40 mU/m²/min) with glucose tracer; muscle biopsies preclamp. If blood sugar at start of the tracer infusion and of the clamp is <60 or >180, the study visit will be concluded without the clamp.

³¹P-MRS optional substudy: DRI pilot funding has been obtained to add a ³¹P-MRS study (method described further below) to the late afternoon preceding each admission to the CTRC for 10 of the MeT1 subjects. On recruitment into MeT1, subjects will be given the option to enroll in this additional sub-study. Specific exclusion criteria for this sub-study will include presence of any metal or other contraindications to MRS, including significant claustrophobia. A separate opt-in section in the consent form will be prepared and submitted to the IRB for this sub-study. Once 10 subjects have opted in and completed, the sub-study will be considered complete and closed to further enrollment. At that point, an interim analysis, including unblinding of these 10 subjects, will be performed. Those who opt in to the sub-study will follow the original study design exactly, with the exception that on day 3 of their study diet, they will be asked to present to the UCD Brain Imaging Center (behind the Leprino Building) in the late afternoon (fasting since lunch; 4-6 hours) for the MRS scan and then proceed to the CTRC for admission for the full study day the following day.

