Though metformin is frequently taken during pregnancy, it is not fully proven safe in pregnancy and we will be excluding subjects who are pregnant or planning to get pregnant. Therefore, a pregnancy test will be done with the initial screening labs, and if a subject is pregnant or breastfeeding, she will be excluded from this study. If a subject becomes pregnant during the study she will be instructed to notify the study coordinator and withdraw from the study.

³¹P-MRS: Subjects may develop claustrophobia in the magnet or mild muscle cramping during the exercise portion

Unforeseen Risks: This study may include risks that are unknown at this time.

E. Potential Scientific Problems:

Interpretation of results/pitfalls and limitations: This study addresses the question of whether metformin affects insulin action and vascular and mitochondrial sequelae of IR in T1D. Based on the literature, I expect that GIR will be increased by this intervention, though it is unclear whether this will be mediated through changes in classical insulin signaling. An improvement in GIR would support the hypothesis that metformin is a viable approach to the treatment of IR in T1D that may have CVD benefits similar to those seen in T2D. If cardiovascular and/or mitochondrial measures improve (with or without changes in IR), this also lends support to metformin as a potentially CVD protective intervention and provides data to support a longer study looking at clinical outcomes. If no change in GIR or vascular measures occurs, this would suggest that IR and CVD risk in T1D are mechanistically different from other populations, an exciting result in itself, and future efforts would explore other mechanisms such as inflammation, sympathetic nervous system activation, and counter-regulatory hormones. Other outcomes will provide hypothesis-generating data to support and direct exploration of these other mechanisms of IR in T1D.

Other potential limitations of this study are:

- (1) Small size: it is possible that a smaller effect will occur in T1D than in other populations and this may therefore be missed in this small sample size.

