- (6) Multiple confounders of an analysis of effect on IR also exist, and every effort will be made to minimize the effect of these confounders including emphasis on a stable activity level throughout the intervention periods and exclusion of highly active subjects. Physical stress will be avoided by rescheduling study days as needed for any illness. Efforts to avoid hypoglycemia will include CGM available to the patient and the PI with insulin dose adjustments as needed. In addition, careful statistical analysis of CGM data will be performed to look for and adjust for any effect of hypoglycemia. If present, this underscores the importance of identifying non-glycemic mechanisms involved in IR as complete normalization of glycemia without

hypoglycemia is unrealistic in T1D, especially in an outpatient, lifelong diabetes regimen. Sex hormones also affect insulin sensitivity in women. The age range of particular clinical interest for this study is primarily middle age, including perimenopausal years in women. I have chosen to include perimenopausal women, but not post-menopausal women in this study. One of my future interests is in the disproportionate increase in CVD risk on premenopausal women with T1D. I have powered the current studies adequately to compare responses to the interventions between genders. I am therefore concentrating on women in which I expect to see sex-based differences, that is those in the pre/perimenopausal stages. Hormonal variation will be dealt with in the usual fashion of scheduling visits during the early follicular phase. Estradiol and FSH levels will be checked with baseline labs on all clamp study days to confirm similar hormone levels at all visits. Other confounders such as emotional stress will be difficult to avoid and are present in any study of this type.

F. Data Analysis Plan:

Data collected from each subject will be verified and entered into a computer database. Confirmation of data quality will be performed using computer programs designed to detect errors using accepted ranges, logic checks, and missing values. Outliers will be checked against the original record, and correct values entered into the final data. Data will be transferred into the SAS System Version 8.0 (SAS Institute, NC) for analysis. We plan to use Redcap for data management and SAS for all statistical analysis. Descriptive statistics of all variables at all time points will be derived and reported.

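### Creatinine and hCG are listed only at screening, before placebo, and the available text lists no recheck before metformin is dispensed at Visit 6, about 8 to 15 weeks after placebo starts

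*Combined protocol and SAP*

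**What the plan says.** The Metformin paragraphs under Risks (section IV.D) name renal insufficiency as a contraindication, because of acidosis, and exclude pregnancy. The exclusion criteria in IV.B set the creatinine limit at 1.5 mg/dl for men and 1.4 mg/dl for women.

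Both tests belong to screening. On pregnancy, the risk text says "Therefore, a pregnancy test will be done with the initial screening labs". The Screening paragraph in IV.B lists β-HCG together with "HbA1c, metabolic panel, TSH, urine microalbumin, and CBC". The blood collection paragraph in IV.D places a chemistry-7 and a pregnancy test at Visit 1.

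Under Study design, subjects "will have a fixed order of treatment (placebo-metformin) and will be given their first medication after screening is complete and eligibility confirmed". Then: "After a two week to two month washout period, the full cycle will be repeated with the second intervention". The Visit 6 entry (Day B1) reads "Insert CGM and receive instruction on use and download, pick up Metformin", followed by dosing instructions. It lists no laboratory test.

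Two provisions bear indirectly on pregnancy. Study design says "Women will be tested at the same time in their menstrual cycle (day 4-9) after each intervention period", and section IV.E, limitation 6, says "Estradiol and FSH levels will be checked with baseline labs on all clamp study days to confirm similar hormone levels at all visits". After screening, a woman who becomes pregnant is to tell the coordinator and withdraw.

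**The concern.** In a fixed-order design, one eligibility check before the first medication is a check before placebo. The drug that carries the renal and pregnancy restrictions comes a full treatment period and a washout later. A subject whose creatinine crosses the limit after Visit 1, or a woman who conceives during the washout, could be given metformin, titrated to as much as 1000 mg twice daily, without a scheduled test to reveal it. This is a matter of patient safety. It does not touch the analysis.

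**Working it through.** **Where the tests appear.** Each place in the text that lists laboratory tests or dispenses drug was compared.

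| Place | Creatinine or chemistry panel | hCG |
|---|---|---|
| Screening, Visit 1 (IV.B; IV.D blood collection) | yes (metabolic panel / chemistry-7) | yes |
| Visit 5, placebo study day (IV.A; IV.D; IV.E item 6) | not named | not named; estradiol and FSH drawn, cycle day 4-9 |
| Visit 6, metformin pick-up (IV.B) | not named | not named |
| Visit 8, metformin study day | not named | not named; same indirect checks as Visit 5 |

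That the screening panel includes creatinine is the standard reading of a metabolic panel or chemistry-7. The text does not spell it out.

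**Interval from placebo start to metformin.** The inputs are the end of the placebo phase (day A43) and a washout of 14 days to two months (taken as 60 days).

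- Shortest: 43 + 14 = 57 days; 57/7 = 8.1 weeks.
- Longest: 43 + 60 = 103 days; 103/7 = 14.7 weeks.
- Counting from A42, or taking two months as up to 62 days, widens this to 42 + 14 = 56 days (8.0 weeks) and 43 + 62 = 105 days (15.0 weeks).

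The time from Visit 1 to day A1 is not stated and adds to the age of the creatinine result. For pregnancy, the interval after the indirect check at Visit 5 is the washout alone, 14 to about 60 days.

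**What an hCG at Visit 6 could detect.** Assume regular 28-day cycles and ovulation near day 14 (neither is in the documents), with A43 and B43 both on cycle day 4 to 9.

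- B43 minus A43 = 28k ± 5 days, so B1 minus A43 = 28k − 42 ± 5.
- k = 2 gives 9 to 19 days, cut to 14 to 19 by the minimum washout. k = 3 gives 37 to 47 days. k = 4 gives 65 to 75 days, beyond two months.
- B1 lies 42 days before cycle day 4 to 9, which is cycle day 18 to 23 (4 + 56 − 42 = 18; 9 + 56 − 42 = 23).
- A conception in the current cycle is then 18 − 14 = 4 to 23 − 14 = 9 days old, and a test may miss it.
- A conception in the preceding cycle is 32 to 37 days old, and the next period would be about 17 to 22 days late.

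So the hCG adds little after a washout of 14 to 19 days and more after one of 37 to 47 days.

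**Expected events.** Forty start and 30 complete, half of them men, so there are 30 to 40 subjects and at most 15 to 20 women. The rates are assumptions without a source in the documents.

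- Pregnancy during the washout, assuming 0.1% to 1% per month: 15 × 0.001 × 14/30.4 = 0.007; 20 × 0.01 × 60/30.4 = 0.39.
- Creatinine crossing the limit, assuming 0.5% to 2% over the interval: 30 × 0.005 = 0.15; 40 × 0.02 = 0.8.

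These count conceptions and threshold crossings. They are not injuries.

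**The case against.** The best defence has four parts.

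First, silence is weak evidence here. The study-day list in the blood collection paragraph is not exhaustive: it omits estradiol and FSH, which IV.E names, and the counter-regulatory hormones and adiponectin, which IV.A names. Potassium is infused to keep its level normal, yet no list names a potassium measurement. Figure 4 and the appendices are not available. This stands. A reader might infer that creatinine is certainly never measured after Visit 1; the documents do not support that, only that no recheck is listed in the text at hand.

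Second, cycle-based scheduling would probably expose a missed period. The team takes a menstrual history at screening and must know cycle dates to place Visit 8, and the plan explains that "Allowing up to 2 months between interventions is necessary to allow this type of scheduling with the possibility of a missed cycle". This largely stands for regular cycles, and it weakens the case for the hCG. It does not remove it: the protocol attaches no test to a late period, and it deliberately includes perimenopausal women, whose cycles may be irregular.

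Third, no rule in the documents says how recent a creatinine result must be, and a Visit 5 result would itself be 14 to about 60 days old at dispensing. That is true, so there is no breach of the plan's own rules. Still, for any one subject the Visit 5 result is 43 days fresher than the present one, plus the unstated gap from Visit 1 to A1.

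Fourth, other safeguards exist. Subjects are screened against essentially the contraindication threshold, those planning pregnancy are excluded, pregnancy must be reported, and the third discontinuation criterion covers contraindications. The protocol also notes that metformin is often used in pregnancy. These lower the risk, but each acts only on what is already known, and none is a test before dispensing.

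**Conclusion.** The point holds as a modest safety gap. On the available text, the renal and pregnancy limits that the protocol ties to metformin are applied once, before placebo, and are not re-applied at first exposure about 8 to 15 weeks after placebo starts. The creatinine part is the firmer one, since nothing in the text bears on renal function between Visit 1 and Visit 6. The pregnancy part is mainly the washout.

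A reader might go further and infer that the plan foreseeably exposes subjects to harm, or that the trial's results are compromised. Neither follows. With the assumed rates, 0.15 to 0.8 creatinine crossings and about 0.01 to 0.4 pregnancies are expected in the whole trial, fewer than one of each, and the rates themselves have no basis in the documents. Power, alpha and bias are untouched. This is a safeguard to consider, not a required correction.

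**What to change.** Re-apply the existing limits before metformin.

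- Run creatinine on the baseline blood already drawn at Visit 5, and review it before Visit 6. The minimum washout leaves 14 days for this.
- At Visit 6, record the last menstrual period and do an hCG in women able to conceive. This matters most when a period is late or irregular, or when the washout spans a further cycle.
- Withhold metformin if the creatinine limit in the exclusion criteria is met or the hCG is positive.

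The cost is about 30 to 40 creatinine tests on an existing draw and 15 to 20 pregnancy tests at an existing visit, with no new visit or threshold. The downside is that a few subjects may be stopped after completing placebo and would then give no paired data; the plan already allows for 40 − 30 = 10 non-completers. A negative hCG would not exclude a very recent conception. If an appendix or Figure 4 already provides a recheck, one sentence in the Visit 6 entry settles the matter.

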The first 3-6 months of the grant period is anticipated to be needed for completion of IRB and CTRC approval processes. Screening

Task	Year 1	Total	Year 2	Total	Year 3	Total
Screening & enrollment		10		25		40
Data collection						
Data entry & analysis						
Manuscript preparation						

and enrollment will start within the first half year and enrollment will proceed at a rate of 1-2 subjects per month. This will allow completion of enrollment by early in the third year and completion of the study by late in the third year.

G. Summarize Knowledge to be gained:

Summary: The above cross-over design study will yield important results regarding the mechanism and vascular consequences of IR in T1D and will help guide future research and clinical care of T1D regardless of the results. If NEFA lowering does improve IR and its vascular correlates, this may become a new therapeutic target in the management of T1D. Further exploration of insulin sensitizing agents vs. NEFA lowering agents will be indicated to determine the optimal intervention for CVD risk management.

H. References:

